Detection and removal of colorectal adenomas is the recommended approach to the prevention of colorectal cancers (CRC). In separate studies we reported that water infusion in lieu of air insufflation (water method) provided a significantly higher overall adenoma detection rate (ADR) and proximal diminutive ADR than the usual method of air insufflation used during scope insertion. When indigocarmine was added to the water method, the dye highlighted small colonic lesions and significantly increased the overall ADR compared with historical cohorts examined by the water method alone or the conventional air method, as well as proximal diminutive ADR when compared with the water method alone. This proposal addresses the question of whether the water method (with or without indigocarmine) will result in a significantly higher proximal diminutive ADR compared with the air method alone in a RCT. The primary hypothesis asserts that a higher proportion with at least one proximal diminutive adenoma (ADR) will be found in the group randomized to the water + indigocarmine method compared with those randomized to the water method alone or the air method. Asymptomatic veterans referred for sedated colonoscopy for CRC screening at the Sacramento VAMC will be considered for enrollment. Over a 2.5 year recruitment period a total of 330 consented veterans will be randomized to confirm a 20% (34% - 14%) difference in proximal diminutive ADR in favor of the water group in the water vs. air comparison; and a 30% (64% - 34%) difference in favor of the indigocarmine + water method in the indigocarmine + water vs. water comparison. Consent covers agreement to undergo colonoscopy by the randomized methods, respond to pre- and post-colonoscopy questionnaires and allow the examination to be recorded for data analysis in a de-identified fashion. The PI, experienced in all three methods, will examine all enrolled patients. To ensure quality performance, all groups are expected to maintain the recommended overall ADR of 25% in male subjects and 15% in female subjects. Applicable human subject protection and adverse event monitoring procedures will be followed. Outcome data will be gathered and monitored prospectively and guarded by relevant data security measures. Appropriate evaluation with logistic regression and analysis of variance will be employed. Population studies showed that traditional air colonoscopy failed to eliminate post screening colonoscopy cancers or cancer mortality in the proximal colon. Even diminutive adenomas harbor significant dysplasia. A simple, inexpensive, easy-to-learn method of adding indigocarmine to the water method may increase the yield of proximal diminutive adenomas. A higher ADR may minimize the burden of interval CRC by decreasing missed adenomas. The long term goal is to perform further studies to determine if post screening colonoscopy interval cancers and cancer mortality in the proximal colon can be attenuated among the veteran population by the novel methods.

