4. **Approach:** Response: We have modified the study protocol to emphasize proximal diminutive adenoma detection as the primary outcome. Instead of involving multiple colonoscopists with variable ADRs, we propose to conduct a single investigator (PI) study. The PI is responsible for pioneering and developing the study method of water infusion in lieu of air insufflation (water method) and the combined chromoendoscopy and water method for screening colonoscopy. In addition, we have added the conventional air method as a control group to compare the results with that of the two investigative methods. We will focus mainly on the group of asymptomatic patients undergoing first time screening colonoscopy. Furthermore, we select the primary outcome as proximal diminutive adenoma detection rate which we consider most relevant in detection and prevention of right-sided colon cancer. We have limited the number of covariates and secondary outcomes. Sample size calculation reveals a total number of 330 subjects are needed (110 in each of three groups). Based on current workload data, we should be able to recruit the required number of patients and complete the study in the 2.5 year recruitment period.

5. Response: We understand it is difficult to blind the investigator and therefore will monitor the quality of the colonoscopy to insure that the three groups of patients are comparable and that the performance of the colonoscopist is consistent with community standard. We expect to maintain an overall ADR of >25% in the air method group as recommended for quality performance. We have just received ACG funding to perform analysis of the video recordings in our previous RCT to discover parameters (e.g. fewer or shorter duration of contractions during withdrawal) that may be associate with increased ADR. We are not proposing such formal analysis in this application because we have yet to develop the criteria for scoring these de-identified video recordings. To include such formal analyses in this proposal risks lowering the feasibility of achieving the proposed objective and weakening this application in the eyes of esteemed critical reviewers. Once these criteria are developed, however, we plan to request IRB approval to subject the recordings in this RCT to similar analysis.

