5-10 mm adenomas and in 1.7% of ≤4 mm adenomas [67]. It is logical to expect that with the adenoma-cancer sequence concept, a proportion of small polyps can grow/evolve to become dysplastic and eventually cancer. Therefore even small lesions especially those on the right side should be biopsied or removed because of the potential risk of future malignancy [7,8]. Once detected on screening colonoscopy and confirmed pathologically, the finding (adenomas or flat lesions) would change the recommendation for subsequent surveillance. The lack of mortality reduction by optical colonoscopy for right-sided cancer has not been explained and this may be related to miss lesions. These considerations justify the detection and removal of diminutive lesions during optical colonoscopy, especially those in the right colon. However, only long term follow up studies will be able to show if removal of the right-sided small adenomas will prevent future development of colon cancer. We will continue to follow this cohort of patients when they return for surveillance colonoscopy or with symptoms of colorectal cancer.

The presence of poor bowel preparation could limit examination. The presence of stool could change the color of the indigo carmine solution turning it green instead of blue color. We emphasize the need for suction removal of the dirty water from the colonic lumen before infusion of clean (colored) water to clear the view for visualization and enhance the staining effects of indigo carmine. Dye staining serves to highlight the contour and contrast between the polyp and adjacent mucosa thus improving observation of the lesions.

Other issues

Issues related to expectation. Expectation of benefit (e.g. finding more lesions) cannot be avoided by the colonoscopist who is not blinded. We'll monitor changes in process variables (variables that reflect the presumed mechanism of treatment, e.g. cecal intubation documented by photograph of the appendix orifice and or cecal folds, withdrawal time, rate of adenoma detection (e.g. control group should meet the quality standard of having an ADR of 25% in male patients undergoing screening).

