Issues related to blinding of endoscopist. The colonoscopist and nurse cannot be blinded to treatment allocation and the primary outcome of proximal diminutive ADR. Randomly selected (10% of total determined by the statistician) coded digital records will be reviewed by independent paid observers to confirm agreement of lesions, cecal intubation, times (endoscopic clock) of insertion, cecal intubation and total withdrawal of the colonoscope. For secondary outcomes, to compensate for increased risk of investigator bias, this study will be designed to use independent, blinded evaluators, whenever indicated, for assessment of outcome(s). No analysis will be started until all patients have completed evaluation to avoid biasing the colonoscopist, who may change the approach if it is known that one group is doing better or worse than the other.

Issues related to male dominance in enrollees. While patients of both sexes will be enrolled, it is likely that there will be a predominance of male enrollees. This is unavoidable because the VA population consists of 95% male and 5% female.

Issue related to differential dropout rate. Since sedation is provided for all groups of patients, we expect the patient tolerance will be similar. Any dropouts will be retained in the data analysis (intent-to-treat) and labeled treatment failures (no adenomas in the unexamined segment) to avoid any differential dropout rate to seriously bias outcomes.

Issues related to the water techniques used to insert the colonoscope lack standardization. The insertion technique for the water method will be standardized (56) by having the air pump turned off until the cecum is reached. Air pockets are suctioned on scope insertion. Dirty water is suctioned before clean water is infused to facilitate scope advancement and to minimize the volume of water inside the patient in case the patient becomes incontinent. Close attention will be paid to keep record of these variables to detect unavoidable variations.

(I) Publication from Last Funding Period (Pertinent Publications)

RESEARCH PAPERS - PEER REVIEWED

[name], Mann S, Leung FW. Option for screening colonoscopy without sedation – a pilot study in United States veterans. *Alimentary Pharmacology and Therapeutics* 2007; 26(4):627-631.

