Risk from time spent in responding to questionnaires: All questionnaires will be kept as concise as possible to minimize the time required to complete them.

Risk from discomfort associated with colonoscopy: Experienced endoscopists will perform and trained personnel will assist in the performance of the colonoscopy.

In addition, the following measures will be implemented to minimize risks for the subjects:

1. Enrollment of subjects will adhere to the inclusion and exclusion criteria.

2. The subjects will be given instructions to notify the study personnel if they have any concerns or untoward symptoms. They will be given the name and phone number of the site investigator and coordinator. An alternative number to one of the research team members will be given to subjects if they are not available. If an adverse event associated with the study should occur, the patients can contact one of the research team members, who will arrange appropriate and timely evaluations.

3. Subjects will be informed of new findings that may affect their decision to remain in the study.

4. VA good clinical practice guidelines will be followed.

5. VA information security measure will be implemented: Written documents and records will be coded so that the identity of the patient is protected. When not in use by the research team, these documents, records and codes will be placed in a locked file cabinet. Key access is available to members of the research team only. All computerized data will be placed in password protected computers. Password access will be available to members of the research team. These procedures are likely effective in protecting confidentiality.

(3) Potential benefit of the Proposed Research to the Subject and Others.

There are no known benefits to the research subjects.

(4) Importance of the Knowledge to be gained.

The result of the study may reveal if the additional dye staining (chromoendoscopy) is more or less efficacious, or no difference compared with the water method or the conventional air method in terms of finding more lesions (polypoid or flat lesions - hyperplastic and adenomatous polyps or cancers).

Therapeutic alternatives: All subjects in the study method group can undergo colonoscopy using the conventional air method.

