The site investigators will perform safety reviews for all patients enrolled in this study on a weekly basis. The site PI of the study is responsible for carrying out continuous monitoring of accrual, data quality, and adverse events. The local study monitoring team will review the accumulating data regarding overall safety and efficacy of treatments employed in the trial. The study monitoring team will meet (twice a year) to review adverse events and subject safety issues.

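### The plan bars any analysis until every patient is evaluated, yet has a local team review accumulating efficacy data and does not say that the review is pooled or kept from the PI

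*Combined protocol and SAP*

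**What the plan says.** Section (4)(g), under the heading on blinding of the endoscopist, accepts that the colonoscopist and nurse know both the allocation and the primary outcome. It then sets a safeguard: "No analysis will be started until all patients have completed evaluation to avoid biasing the colonoscopist, who may change the approach" on learning that one group is doing better or worse than another.

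The Colonoscopy and Colonoscopist paragraphs of section (4)(b) make the PI the only operator.

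Human Subjects section (5), under performance and frequency of safety reviews, says: "The local study monitoring team will review the accumulating data regarding overall safety and efficacy of treatments employed in the trial". The same paragraph gives the PI continuous monitoring of accrual, data quality and adverse events. It gives the monitoring team two meetings a year, on adverse events and subject safety.

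Section (4)(g), on expectation, adds that process variables will be monitored, among them the "rate of adenoma detection (e.g. control group should meet the quality standard of having an ADR of 25% in male patients" having screening examinations).

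**The concern.** The primary outcome is whether at least one proximal diminutive adenoma is found. It depends on how carefully one unblinded person looks. The plan recognises this, and the bar on analysis is its stated protection against that person learning how the arms compare. A review of accumulating efficacy data could supply that knowledge. If compiled arm-level detection results reached the PI, inspection effort could shift between arms, and the final comparison could not separate such a shift from an effect of the method.

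**Working it through.** No figure in the plan is in dispute, so the check sets the passages side by side. One calculation at the end shows how far the fix can reach.

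**1. Whom the bar protects.** It protects the colonoscopist. Section (4)(b) makes that the PI for all cases.

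**2. Whether the reviews overlap in time.** A review of accumulating data takes place, by its own terms, before all patients are evaluated. The bar covers exactly that period.

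**3. When the two statements can both hold.** Either the efficacy review is pooled over arms, or it is by arm but done by people who neither include the PI nor report to the PI. The documents state neither. The team is called local, and its members are not listed. The data-access rules do not settle it: for locked paper records, "Key access is available to members of the research team only", and the password rule in section (5) is similar. These are confidentiality rules and draw no line between the PI and the rest of the team.

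**4. What narrows the reading.** The twice-yearly meeting is limited to adverse events and safety, and the PI's listed duties omit efficacy. The efficacy review therefore has no stated date, format or comparison.

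**5. The adenoma detection rate (ADR) check.** A control-group ADR is an arm-level figure and cannot be read from pooled data. But it is overall ADR, whereas the primary outcome is proximal diminutive ADR, and it compares one arm with an external 25% floor. It is a secondary point of tension and does not contradict the bar outright.

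**6. What the efficacy review would feed.** The documents give no stopping rule, sample-size re-estimation or alpha adjustment. No planned decision depends on it.

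**7. Reach of the fix.** The PI could keep an informal tally without any committee. Inputs are the planning rates in the sample size section: air 0.14, water 0.34, water plus dye 0.64, with 110 per arm. Treating the counts as independent binomials with n per arm, the chance that the true counts already stand in the expected order is

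P(X_air < X_water < X_dye) = Σ_w P(X_water = w) × P(X_air < w) × P(X_dye > w).

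| n per arm | Expected counts (air, water, dye) | Probability of strict order |
|---|---|---|
| 22 (one fifth of 110) | 3.1, 7.5, 14.1 | 0.893 |
| 55 (half of 110) | 7.7, 18.7, 35.2 | 0.991 |

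The expected counts are n × rate, for example 55 × 0.34 = 18.7. The two values of n are illustrative. If the planning rates hold, the order would probably be visible to an attentive operator early on. This limits what the fix can achieve. It is not evidence of harm from the efficacy review.

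**The case against.** The strongest reply is that a consistent reading exists. The bar is the specific rule on analysis, while the efficacy phrase is general oversight wording under a safety heading, with no schedule or output. Monitoring is also not the same as analysis. This stands in part: the passages may be meant consistently. But the stated reason for the bar is knowledge of which group is ahead, and an arm-level listing gives that knowledge without any test. The text has to rule that out, and it does not.

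Second, the PI does every case and reads every pathology report (section (4)(f), follow-up care), and expects the ordering from the pilot data. So the added harm may be small. This stands as a limit. The plan nevertheless thought the bar worth having with an unblinded operator, and a compiled result is firmer than an impression.

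Third, the video check might be thought to cover the risk: "Randomly selected (10% of total determined by the statistician) coded digital records will be reviewed by independent paid observers". It tests agreement on lesions, cecal intubation and times. It does not govern who sees interim results.

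Fourth, subjects are promised new findings that bear on their decision to stay in the study (section (2)(b), item 3). That promise does not depend on an interim efficacy review.

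A reader might infer more from other passages:

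- The Abstract says "Outcome data will be gathered and monitored prospectively and guarded by relevant data security measures". That may mean no more than data capture.
- The Abstract also says "all groups are expected to maintain the recommended overall ADR of 25% in male subjects and 15% in female subjects", and the response to Critique 1, item 5, says "We expect to maintain an overall ADR of >25% in the air method group as recommended for quality performance". Both state expectations. Neither schedules a by-arm tabulation during enrolment.
- Table 7 is a preliminary by-arm analysis of a different ongoing trial. It does not show what will happen in this one.

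**Conclusion.** The point holds as an unreconciled conflict in the current text. A bar meant to keep the sole, unblinded operator from learning how the arms compare sits beside a review of accumulating efficacy data that is not stated to be pooled, independent of the PI or withheld from the PI. The control-group ADR check is a lesser instance of the same gap.

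The documents give no size for the bias, and none is claimed here. A reader might infer twice-yearly looks at efficacy by arm, or an inflated type I error from repeated testing. The documents support neither: the twice-yearly meeting concerns safety, and no interim test is planned. Nor do they show that the PI would receive efficacy results. They only fail to exclude it.

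The conclusion rests on two readings: that accumulating data means data before the last patient is evaluated, and that the bar is aimed at knowledge of relative performance, as its own wording says.

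**What to change.** 1. In the paragraph on performance and frequency of safety reviews, remove efficacy from what the monitoring team reviews, so that review before completion covers safety, accrual and data quality. If the sponsor wants an interim efficacy review, assign it to a named group independent of the PI, and reword the bar in section (4)(g) to allow it.
2. In that paragraph and in the section on blinding of the endoscopist, state that no compiled arm-level detection result is given to the PI or the endoscopy team before the last patient is evaluated. State also that safety, accrual, data-quality and process monitoring fall outside the bar.
3. If the control-group ADR check in the section on expectation is kept during the trial, have someone other than the PI hold it.

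The cost is protocol wording, with no extra patients and no change to the analysis. The downside is that the PI would not see compiled arm-level ADR while the trial runs, so the PI could not act directly on a low control-arm figure. After the change, the report could state that no compiled interim result was given to the operator. It could not state that the operator had no impression of how the arms compared.
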